1.3.3. Early Termination and Follow-up

If study intervention is permanently discontinued, the participant will be asked to remain in the study after the Follow-up visit without study intervention and continue to comply with study visit schedules for approximately 2 years or until study end, whichever occurs first. Refer to Section 4.1 for further details.

Procedure	ET	28-Day Follow-up	6-Month Follow-up	Notes
Visit Identifier	NA	18	19	
Day	NA	EOS 28 days after last dose	182 days after discontinuation for neurological or auditory adverse event	
Visit Window (±Days)	+7	±7	±30	ET visit will be performed on the last day the participant takes the study intervention or as soon as possible thereafter. Follow-up visit is 28 days after last dose. 6-Month Follow-up visit occurs 6 months after the last dose of study intervention for any participant who discontinues the study due to a neurological or auditory adverse event (See Section 10.7).
Medical Procedures				
Full physical examination, including dermatological full body examination	X			See Section 8.2.1 .
Targeted physical examination		X	X	See Section 8.2.1 .
Neurological examination by a neurologist	X		X (see Note)	See Section 10.7.2 for follow-up assessment of participants who discontinue due to a neurological adverse event. Neurological examination will include the Neuropathy Assessment. Refer to the Manuals for General Neurological and Neuropathy Assessments for more information. See Section 8.2.5 . Neurological examination not collected during ET visit for participants who have completed the Month 15E visit, unless these assessments are relevant to the reason for discontinuation. If neurological examination required, the same neurologist who saw the participant for the first 24 months should also do the consultation when possible.
Vital Signs	X	X	X	See Section 8.2.2 .

Procedure	ET	28-Day Follow-up	6-Month Follow-up	Notes
Visit Identifier	NA	18	19	
Day	NA	EOS 28 days after last dose	182 days after discontinuation for neurological or auditory adverse event	
Visit Window (±Days)	+7	±7	±30	ET visit will be performed on the last day the participant takes the study intervention or as soon as possible thereafter. Follow-up visit is 28 days after last dose. 6-Month Follow-up visit occurs 6 months after the last dose of study intervention for any participant who discontinues the study due to a neurological or auditory adverse event (See Section 10.7).
12-lead ECG	X			See Section 8.2.4 . 12-lead ECG is not to be collected during ET visit for participants who have completed the Month 15E visit.
Weight	X			See Section 8.2.1 .
Audiological Evaluation	X		X (see Note)	Audiology and, if applicable, BAEP evaluations should be done on the same day, with audiology assessment first. If they cannot be done on the same day, assessments must be within 7 days of each other. Refer to the Audiology Study Guide for information on the auditory testing. Section 8.2.6 . See Section 10.7.2 for follow-up assessment of participants who discontinue due to an auditory adverse event. Note: Assessments as relevant to the reason for discontinuation

Procedure	ET	28-Day Follow-up	6-Month Follow-up	Notes
Visit Identifier	NA	18	19	
Day	NA	EOS 28 days after last dose	182 days after discontinuation for neurological or auditory adverse event	
Visit Window (±Days)	+7	±7	±30	ET visit will be performed on the last day the participant takes the study intervention or as soon as possible thereafter. Follow-up visit is 28 days after last dose. 6-Month Follow-up visit occurs 6 months after the last dose of study intervention for any participant who discontinues the study due to a neurological or auditory adverse event (See Section 10.7).
BAEP Evaluation	X		X (see Note)	Audiology and BAEP evaluations should be done on the same day, with audiology assessment first. If they cannot be done on the same day, assessments must be within 7 days of each other. Refer to the Manual for BAEP Evaluation. Section 8.2.7 . See Section 10.7.2 for follow-up assessment of participants who discontinue due to an auditory adverse event. Note: Assessments as relevant to the reason for discontinuation. BAEP evaluation not collected during ET visit for participants who have completed the Month 15E visit, unless these assessments are relevant to the reason for discontinuation.
Laboratory				
Hematology and Serum Chemistry	X	X		For participants who have completed the Month 15E visit, creatine kinase will not be tested. Section 8.2.10 and Section 10.2 .
Fasting Lipid Panel	X			Fasting lipid panel is not to be collected during ET visit for participants who have completed the Month 15E visit. Section 8.2.10 and Section 10.2 .
Urinalysis	X	X		For participants who have completed the Month 15E visit, urinalysis will be performed only if considered clinically indicated by the investigator during ET and Follow-up visits. See Section 8.2.10 and Section 10.2 .

Procedure	ET	28-Day Follow-up	6-Month Follow-up	Notes
Visit Identifier	NA	18	19	
Day	NA	EOS 28 days after last dose	182 days after discontinuation for neurological or auditory adverse event	
Visit Window (±Days)	+7	±7	±30	ET visit will be performed on the last day the participant takes the study intervention or as soon as possible thereafter. Follow-up visit is 28 days after last dose. 6-Month Follow-up visit occurs 6 months after the last dose of study intervention for any participant who discontinues the study due to a neurological or auditory adverse event (See Section 10.7).
Pregnancy test (WOCBP only)	X	X		See Section 8.2.13 , Section 10.2 and Section 10.4 .
HBVDNA (applicable countries)	X			Only for participants who were enrolled with a positive HBcAb and a negative HBVDNA in those regions for which hepatitis B prevalence has been reported at a rate of >5.0% or if required by local standard of care. See Section 8.2.10.3 and Section 10.6 .
Skin punch biopsy for evaluation of axonal dystrophy and IENFD	X		X (see Note)	See Section 8.2.8.1 . See Section 10.7.2 for follow-up assessment of participants who discontinue due to a neurological adverse event. Note: Assessments as relevant to the reason for discontinuation. Skin punch biopsies will not be collected during ET visit for participants who have completed the Month 24 visit.
Trial treatment				
Study intervention accountability and compliance	X			See Section 6.2 and Section 6.4 .
Clinical assessments				
SALT	X			See Section 8.1.2.1 .
Non-AA SALT	X			Only participants with other known etiologies of scalp hair loss in addition to AA. See Section 8.1.2.1.1 .
C-SSRS	X			See Section 8.2.11.1 .

Procedure	ET	28-Day Follow-up	6-Month Follow-up	Notes
Visit Identifier	NA	18	19	
Day	NA	EOS 28 days after last dose	182 days after discontinuation for neurological or auditory adverse event	
Visit Window (±Days)	+7	±7	±30	ET visit will be performed on the last day the participant takes the study intervention or as soon as possible thereafter. Follow-up visit is 28 days after last dose. 6-Month Follow-up visit occurs 6 months after the last dose of study intervention for any participant who discontinues the study due to a neurological or auditory adverse event (See Section 10.7).
Patient reported outcomes				
PGI-C	X			See Section 8.1.3.1 .
Other				
Prior and current concomitant medication(s) and treatment(s) monitoring	X	X	X	See Section 6.5 .
Adverse event monitoring	X	X	X	See Section 8.3 and Section 10.3 .
Contraception check for WOCBP	X	X		See Section 5.3.1 and Section 10.4 .

Abbreviations: AA = alopecia areata; BAEP = brainstem auditory evoked potential; ECG = electrocardiogram; EOS=end of study; ET = Early Termination; HBcAb = hepatitis B core antibody; HBVDNA = hepatitis B viral deoxyribonucleic acid; IENFD = intraepidermal nerve fiber density; PGI-C = Patient's global impression of change; SALT = Severity of Alopecia Tool; WOCBP = women of childbearing potential.

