2.2.1. Nonclinical Studies

Data from nonclinical studies support the planned clinical trials with PF-06651600; these studies are described in the Investigator's Brochure (IB).

In the first 9-month study of PF-06651600 in dogs, bilateral axonal dystrophy (not axonal degeneration) in the olivary nuclei of the brainstem was observed in males and females administered ≥ 20 mg/kg/day. Auditory testing (BAEP) performed on recovery control and high dose animals during the last 2 weeks of the 3-month recovery period showed BAEP waveform defects. There was partial recovery in the brainstem microscopic lesions at the end of the 3-month recovery period. The no observed adverse effect level (NOAEL) was the lowest dose tested of 5 mg/kg/day, based on the adverse finding of axonal dystrophy in the brainstem and associated waveform defects in males and females administered ≥ 20 mg/kg/day.

In the second 9-month study in dogs, PF-06651600-related, minimal to moderate axonal dystrophy (axonal swelling due to neurofilament accumulation without evidence of axonal degeneration) in the brainstem, minimal axonal dystrophy in the sciatic nerve and branches of the vagus nerve, and an increased severity (from minimal to mild) of axonal dystrophy in the spinal cord were observed at ≥ 20 mg/kg/day (a 12-fold exposure multiple relative to the clinical dose of 50 mg). Minimal to mild axonal dystrophy was also observed in the white matter of the rostral vermis of the cerebellum at ≥ 10 mg/kg/day. Adverse BAEP findings were noted in 1 male and 1 female administered 40 mg/kg/day (a 29-fold exposure multiple relative to the clinical dose of 50 mg) at 7 and/or 9 months of dosing, and these findings completely recovered at the end of the 6-month recovery in the animal that continued into the recovery phase. The auditory deficits observed were consistent with a central, not peripheral, effect on auditory function.

The NOAEL was 10 mg/kg/day, based on adverse over-immunosuppression and axonal dystrophy in the central and peripheral nervous system at ≥ 20 mg/kg/day and accompanied by auditory deficits (BAEP) at the highest dose of 40 mg/kg/day. The area under the concentration-time curve (AUC) exposure margins in this study at the NOAEL at study end were approximately 1.5x and 6.5x relative to the predicted exposure at the 200 mg and 50 mg clinical QD doses, respectively (Table 1).

PF-06651600 bioequivalence between tablets and capsules was established in completed Phase 1 Study B7981029.

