7.1.1.1. Observation Period

Participants will be asked to remain in the study after the Follow-up visit without study intervention. The Period during which participants are in the study after having permanently discontinued study intervention is referred to as the Observation Period. During this period participants will continue to comply with study visit schedules for approximately 2 years or until study end, whichever occurs first. At visits during the Observation Period, only the SALT, PGI-C, and concomitant medications/treatments will be collected at the visits specified in the applicable SoAs in Section 1.3.2; AE and SAE reporting will follow the guidelines in Section 8.3.

Participants will complete the final visit in the Observation Period approximately 2 years after the last dose of study intervention or at study end whichever occurs first as follows:

- at the protocol-scheduled visit 24 months after the last dose of study intervention, OR
- at the next scheduled visit after the 24-month time point (if no scheduled visit falls at the 24-month time point), OR
- at study end.

For example, if the last dose of study intervention occurs around the time of Month 22E then the final visit in the Observation Period would be conducted at Month 51E (ie, the next closest scheduled visit occurring 24 months after Month 22).

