8.3.1. Time Period and Frequency for Collecting AE and SAE Information

The time period for actively eliciting and collecting AEs and SAEs (“active collection period”) for each participant begins from the time the participant provides informed consent, which is obtained before the participant’s participation in the study (ie, before undergoing any study-related procedure and/or receiving study intervention), through and including a minimum of 28 calendar days, except as indicated below, after the last administration of the study intervention.

The time period for actively eliciting and collecting AEs and SAEs (“active collection period”) for each participant begins from the time the participant provides informed consent, which is obtained before the participant’s participation in the study (ie, before undergoing any study-related procedure and/or receiving study intervention), through and including Visit 19.

Follow up by the investigator continues throughout and after the active collection period and until the AE or SAE or its sequelae resolve or stabilize at a level acceptable to the investigator, and Pfizer concurs with that assessment.

For participants who are screen failures, the active collection period ends when screen failure status is determined.

If the participant withdraws from the study and also withdraws consent for the collection of future information, the active collection period ends when consent is withdrawn.

If a participant definitively discontinues or temporarily discontinues study intervention because of an AE or SAE, the AE or SAE must be recorded on the CRF and the SAE reported using the CT SAE Report Form.

Investigators are not obligated to actively seek AEs or SAEs after the participant has concluded study participation. However, if the investigator learns of any SAE, including a death, at any time after a participant has completed the study, and he/she considers the event to be reasonably related to the study intervention, the investigator must promptly report the SAE to Pfizer using the CT SAE Report Form.

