#### 3.6.1. Adverse Events

- The following risk period (RP) will be applied for TP1
  - For patients who entered TP1 and continued into TP2, RP is defined from date of 1st dose of TP1 to min (date of 1st dose of TP2 - 1, date of the last dose of TP1 + 35). This RP excluded AEs starting on the same day of 1st dose of TP2 or AEs starting on any day in TP2.
  - For patients who entered in TP1, permanently discontinued from study (and did not enter in TP2), RP is defined from date of 1st dose of TP1 to min (date of last contact, date of the last dose of TP1 + 35), where last contact date is min (date of discontinuation of study, date of data cut-off), if a subject dies, the death date will be the last contact date.
- The following risk period will be applied for TP2
  - For patients who entered TP2 and continued into TP3, RP is defined from date of 1st dose of TP2 to min (date of 1st dose of TP3 - 1, date of the last dose of TP2 + 35). This RP excludes AEs starting on the same day of 1st dose of TP3 or AEs starting on any day in TP3

- For patients who entered in TP2 and, directly entered in the Observation Period or permanently discontinued from study (and did not enter in TP3), RP is defined from date of 1st dose of TP2 to min (date of last contact, date of the last dose of TP2 + 35), where last contact date is min (date of discontinuation of study, date of data cut-off), if a subject dies, the death date will be the last contact date. This RP extends 35 days into the observation period.
- The following RP will be applied for Observation Period for patients who entered from TP2
  - For patients who entered the observation period from TP2, RP is defined from date of last dose + 1 to the last contact date, where the last contact date is min (date of discontinuation of study, date of data cut-off). If a subject dies, the death date will be the last contact date. This RP excludes AEs starting while on-drug.
- The following RP will be applied for TP3

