**Table 3. Groups**

Period	Groups
Placebo-controlled phase (TP1)	
 
• Ritlecitinib 200/50 mg QD
 
• Placebo
 

Active therapy extension phase (TP2)	
 
• Ext Ritlecitinib 50 mg QD
 
• Ext Ritlecitinib 200/50mg QD
 

Overall (TP1+TP2)	
 
• Ritlecitinib 200/50/50 mg QD
 
• Any Ritlecitinib
 
• Any Ritlecitinib + Placebo (Total)
 

For tables summarizing data by visit (such as BAEP, skin punch biopsy endpoints and efficacy endpoints), which only include data from TP1 in the PCD-CSR, the following groups will be summarized:

- Ritlecitinib 200/50 mg QD
- Placebo

For other tables such as dispositions, demographic and baseline characteristics, medical history, primary diagnosis, prior medications and compliance the groups to be summarized will be:

- Ritlecitinib 200/50 mg QD
- Placebo → Ritlecitinib 200/50 mg QD.

## 8.2. Supplemental CSR 1

The supplemental CSR 1 will be prepared after the last participant completes the 4-week follow-up visit, or the Month 15E visit (TP2) if the last participant is enrolled in TP3, whichever is later. This CSR will include:

- Efficacy through Month 15E (TP1+TP2). Efficacy data from participants while they are on the Observation Period will not be included in the summaries of efficacy. Instead, listings and plots may be provided.
- All safety data collected through the cut-off date for this CSR (including the Follow-up Period and the Observation Period).

For summaries in this CSR, the groups will be the following:

- For duration of treatment, concomitant medication, lab abnormality, lab values meeting discontinuation criteria, vital signs/QTcF values meeting pre-specified criteria and AE tables.

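### AEs are collected to the 6-month neurological/auditory follow-up visit, but SAP 3.6.1 gives participants who leave in TP1 no risk period after last dose + 35 days

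*Protocol*

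**What the plan says.** **Collection.** Protocol 1.3.3 places Visit 19 at "182 days after discontinuation for neurological or auditory adverse event", with a ±30-day window and AE monitoring marked. The note in the same table counts from the last dose: "6-Month Follow-up visit occurs 6 months after the last dose of study intervention for any participant who discontinues the study". Protocol 8.3.1 has two paragraphs on how long AEs are actively collected. One runs "through and including a minimum of 28 calendar days, except as indicated below, after the last administration of the study intervention"; the other runs "through and including Visit 19". For participants off drug in the Observation Period, Protocol 7.1.1.1 says that "AE and SAE reporting will follow the guidelines in Section 8.3".

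**Risk periods.** For a participant who leaves in TP1, SAP 3.6.1 ends the risk period at "min (date of last contact, date of the last dose of TP1 + 35". The TP2 and TP3 risk periods carry the same 35-day cap, but the SAP adds Observation Period risk periods, from the day after the last dose to last contact, for entrants from TP2 and from TP3. It writes none for entrants from TP1.

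**Reporting.** SAP 8.2 says supplemental CSR 1 will contain "All safety data collected through the cut-off date for this CSR (including the Follow-up Period and the Observation Period". Table 4, which governs the AE tables in that report, has TP1 columns for ritlecitinib and placebo, and an Overall column covering the three treatment periods and the Observation Period. None of the three groups under Overall is placebo alone.

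**The concern.** Visit 19 exists for participants who stopped because of the kind of event this trial was set up to study. Asking sites to record AEs up to that visit implies that those AEs have a place in the report. For someone who stopped in TP1, the SAP assigns no risk period to an AE that begins after day 35, although it does so for comparable participants who stop in TP2 or TP3 and go into observation.

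TP1 is the only part of the trial with a concurrent placebo group. A new neurological or auditory event some months after stopping in TP1 could not be set against placebo in any planned AE table, and a programmer would have to guess whether it belongs under Overall.

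**Working it through.** No power or precision figure bears on this point. The check sets the rules side by side and counts days.

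**Inputs**
- Visit 19 at day 182, window ±30 days, so days 152 to 212 (Protocol 1.3.3). Last dose is taken as day 0. The schedule uses both discontinuation and last dose as the anchor; I assume they coincide.
- TP1 leaver risk period ends by day 35 at the latest (SAP 3.6.1).
- AE collection runs to Visit 19 (Protocol 8.3.1, second paragraph). The first paragraph carries an exception clause, and the schedule marks AE monitoring at Visit 19, so this is the natural reading.

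**Days outside every defined risk period, TP1 leaver.** Uncovered days = Visit 19 day − 35; share = uncovered ÷ Visit 19 day.

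| Visit 19 on | Uncovered days | Share |
|---|---|---|
| Day 152 | 152 − 35 = 117 | 117/152 = 77.0% |
| Day 182 | 182 − 35 = 147 | 147/182 = 80.8% |
| Day 212 | 212 − 35 = 177 | 177/212 = 83.5% |

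These are shares of calendar time, not of events.

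**Who is covered after day 35**

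| Participant | Defined risk period after day 35 |
|---|---|
| Leaves in TP1 | None |
| Leaves in TP2 or TP3, enters the Observation Period | Yes, to last contact (days 1 to 35 fall in two periods) |
| Leaves in TP2 or TP3, attends Visit 19 outside the Observation Period | None, if that status exists |

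The last row depends on protocol text that conflicts. Protocol 10.7.2 withdraws participants who meet its criteria from the study after the Early Termination and Follow-up visits. Protocol 1.3.3 and 7.1.1.1 ask those who permanently stop study intervention to remain.

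**Does the Overall column close the gap?** SAP 3.6.1 refers the CSR 1 TEAE summaries to Table 4, but no risk period is written for Overall.
- If Overall is the union of the defined risk periods, late events in TP1 leavers drop out.
- If Overall means everything up to the cut-off, they are counted. A placebo participant who left in TP1 would then appear only in the combined total, because no Overall group is placebo alone.

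On both readings the TP1 columns stop by day 35. Table 3, for the PCD-CSR, has an Overall of TP1 and TP2 only, although SAP 8.1 also promises all safety data to the cut-off.

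**The case against.** The strongest answer is that a last-dose-plus-35-day window for treatment-emergent events is a legitimate choice and that little is lost outside it. Most of that stands.

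- **Already counted.** Incidence is the number and percentage of participants with an event, and risk periods work on start date. A participant at Visit 19 has already stopped for a neurological or auditory AE. If that event began on drug or by day 35, it counts as treatment-emergent however long it lasts. Only a new, later event is at issue.
- **Other routes.** SAP 6.7 provides subject listings, SAP 6.7.1 reports adjudication data separately, and SAP Appendix 1 keeps a 6-Month Follow-up label for by-visit safety data.
- **Timing.** The risk periods entered the SAP in version 5.0 (April 2023), while version 4.0 (August 2022) already refers to analyses added to the PCD-CSR. That report probably preceded them, so the remedy belongs in the supplemental reports.

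A reader might infer that these events enter no AE summary at all. The documents do not establish that: SAP 8.2 and the Overall column may include them. Nor do all risk periods stop at day 35, since Observation Period entrants from TP2 and TP3 are followed to last contact.

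A reader might also take the dog data as evidence of delayed onset. In the first 9-month study, testing "during the last 2 weeks of the 3-month recovery period showed BAEP waveform defects", but Protocol 2.2.1 describes auditory testing in that study only at that time, so onset cannot be dated. In the second, the findings appeared during dosing and recovered in the animal that was followed. This fits persistence at least as well as late onset.

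None of this supplies a risk period for the TP1 leaver or a table with a placebo group.

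**Conclusion.** The point holds in a limited form. New-onset AEs from day 36 to Visit 19 in participants who leave in TP1 are to be collected but fall in no defined risk period and in no AE table with a placebo group. The gap is 147 of 182 days at the nominal visit, and 117 to 177 days across the window. Whether CSR 1's Overall column counts them is undefined.

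The effect is that late off-treatment events can be understated. To call this a bias toward safety would go beyond the documents. They do not say how many participants will leave TP1 for these reasons; in a trial of about 60 the number is likely to be small, and those participants are usually counted already for the event that made them stop.

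The conclusion assumes that the Visit 19 paragraph of Protocol 8.3.1 governs collection for these participants, and that discontinuation and last dose fall on the same day. For TP2 and TP3 leavers, a gap arises only if someone can attend Visit 19 without being in the Observation Period, which the protocol leaves unclear.

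**What to change.** 1. In SAP 3.6.1, add a post-treatment risk period for TP1 leavers, and for any TP2 or TP3 leaver not in the Observation Period. Run it to Visit 19 or last contact, whichever is later, within the data cut-off. Name Visit 19 explicitly: last contact for TP1 and TP2 leavers is tied to the date of study discontinuation, which under Protocol 10.7.2 could come before that visit.
2. Show events starting after day 35 in a separate off-treatment column, number and percentage, by initial treatment group with placebo shown on its own. Leave the TEAE tables unchanged. TP1 and TP2 leavers belong in CSR 1, TP3 leavers in CSR 2. SAP 8.3 currently pools all participants in CSR 2, so the split there needs to be stated.
3. State the risk period behind the Overall column in Table 4.
4. Reconcile the two collection paragraphs in Protocol 8.3.1, the two anchors for Visit 19 in Protocol 1.3.3, and Protocol 10.7.2 with 1.3.3 and 7.1.1.1 on whether these participants remain in the study.

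With item 1 in place, the 147 uncovered days fall to 0. The cost is one SAP definition and one small table per supplemental report, plus the clarifications. The drawback is a sparse column, which may be empty.
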